## 8 STUDY ASSESSMENTS AND PROCEDURES

### 8.1 EFFICACY ASSESSMENTS

There are no efficacy assessments for this Phase 1, FIH, clinical study.

### 8.2 SAFETY AND OTHER ASSESSMENTS

Planned time points for all safety and other assessments are provided in the SoA (see Section 1.3).

#### 8.2.1 PHYSICAL EXAMINATION

- A complete physical examination will include assessments of general appearance, skin; head/neck; pulmonary, cardiovascular, gastrointestinal, external genitourinary (optional), lymphatic, and musculoskeletal systems; extremities; eyes (inspection and vision control); ears, nose; throat; and neurologic status.
- An abbreviated physical examination will include assessments of general appearance; head, ears, eyes, nose, and throat; cardiovascular; respiratory; and gastrointestinal systems (including the abdomen).
- A targeted physical examination may be conducted at any time at the Investigator's discretion and should be limited to systems of clinical relevance (ie, cardiovascular, respiratory, lymph nodes, liver.)

#### 8.2.2 HEIGHT AND WEIGHT

Height (cm) will be measured only at Screening. Weight will be measured in kilograms according to the SoA (Section 1.3).

#### 8.2.3 VITAL SIGNS

Oral, tympanic or temporal body temperature, respiratory rate, pulse, and systolic and diastolic blood pressure will be assessed. The method of body temperature assessment chosen should be recorded and consistent throughout the study.

If oral temperatures (°C) are taken, participants will have had no food or liquid for at least 5 minutes before assessment.

During the infusion, systolic/diastolic blood pressure and pulse should be measured in a semi-spine/semi-reclined position. For all other readings, blood pressure and pulse will be taken in a supine position after 10 to 15 minutes rest.

Respiratory rate (breaths/min) will be taken after at least 5 minutes rest; breaths are counted for 30 seconds and multiplied by 2. Respiration rate will be taken concurrently with all ECGs. During the infusion, respiration rate will be taken in a semi-supine/semi-reclined position.

---

#### 8.2.4 ELECTROCARDIOGRAMS

Participants will undergo telemetry beginning on Day -1 through 50 hours after the start of infusion ([Table 8](#)). Five-minute telemetry data extraction periods should begin after 10 minutes of rest in a semi-reclined position, and when applicable, at least 15 minutes prior to the nominal PK/ADA/nAb blood collection time point and to allow completion of the ECGs prior to collection of PK/ADA/nAb sample.

Standard 12-lead ECGs will be recorded after the participant has been resting at least 10 minutes using a CAM-14 module. Single ECGs will be collected at the time points noted in the SoA (Section [1.3](#)). Additional ECGs will be performed at the discretion of the Investigator.

Telemetry and ECG readings will be performed in a supine position after the allotted time specified above. During the infusion, procedures will be performed in a semi-supine/semi-reclined position.

The Investigator will be responsible for reviewing the ECG to assess whether the ECG is within the reference limits and to determine clinical significance of the results. If necessary, the Investigator has the right to override the interpretation and intervals as measured by the ECG machine. The ECG will be assessed for the following measures: P wave, QRS complex, U wave, QRS duration, QT interval, QTcF, T wave, ST segment, RR interval, PR interval, and qualitative results.

---

#### 8.2.5 CLINICAL LABORATORY EVALUATIONS

Clinical laboratory assessments will be collected under appropriate conditions defined by the clinical unit's standard of practice.

- The research laboratory unit will be used to perform all clinical laboratory tests including serum pregnancy test, which will be assessed by the CRU staff. The Investigator should take immediate action for any safety concerns based on laboratory results.
- The Investigator must review the laboratory report, document this review, and record any clinically relevant changes occurring during the study in the eCRF. The laboratory reports must be filed with the source documents. Clinically significant abnormal laboratory findings are those that are not associated with an underlying disease, unless judged by the Investigator to be more severe than expected for the participant's condition.

- All laboratory tests with values considered clinically significantly abnormal during participation in the study, including the participant's last EOS visit, should be repeated until the values return to normal or Baseline or are no longer considered clinically significant or follow-up is no longer needed per the judgment of the Investigator or Medical Monitor.
  - If such values do not return to normal/Baseline within a period of time judged reasonable by the Investigator, the etiology should be identified, and the Sponsor notified.
- All protocol-required laboratory assessments, as defined in [Appendix 1](#), must be conducted in accordance with the Laboratory Manual and the SoA (Section [1.3](#)).

Blood volumes for laboratory samples will be included in the Laboratory Manual.

### 8.3 PHARMACOKINETICS

Whole blood samples will be collected for measurement of serum concentrations of XTMAB-16 ([Table 8](#)). Instructions for the collection and handling of biological samples will be provided by the Sponsor in a separate Laboratory Manual. The actual date and time (24-hour clock) of each sample will be recorded in the eCRF. Samples will be used to evaluate the serum concentration and PK of XTMAB-16. Each serum sample will be divided into 2 aliquots (1 each for primary and back-up).

Measurement of concentrations of XTMAB-16 will be performed using a validated assay method by or under the supervision of the Sponsor. The analytical methods used to measure concentrations of XTMAB-16 will be described in a separate bioanalytical report. Only samples that are within the window of sample stability will be analyzed.

While PK samples must be collected from participants assigned to the placebo arm to maintain the blinding of treatment assignment, PK assay results for these participants are not needed for the safety conduct or proper interpretation of this trial and most samples will therefore not be analyzed. Personnel responsible for performing PK assays will be unblinded to participants' treatment assignments to identify appropriate PK samples to be analyzed. Samples from participants assigned to placebo may be analyzed upon request (ie, to evaluate a possible error in dosing).

Blood samples for PK/ADA/nAb will be collected for analysis from participants who experience an SAE that is also considered related to study treatment. If an SAE occurs prior to the validation of the XTMAB-16-specific PK assay, blood samples in these potential cases will be analyzed using the infliximab assay, as needed, on an individual basis. These samples from these participants will be re-analyzed as part of the batch analyses using the validated XTMAB-16-specific assay prior to completion of the study.

Blood volumes for PK samples will be included in the Laboratory Manual.

**Table 5 List of Pharmacokinetic Parameters and Definitions**

Parameters	Definition/Calculation
$C_{max}$	Maximum observed serum concentration
$C_T$	Serum concentration observed at the end of drug infusion, where T is the duration of infusion time
$t_{max}$	First time to reach $C_{max}$ after drug administration
$AUC_{0-t}$	Area under the serum concentration versus time curve from time zero to the last quantifiable time point at t
$AUC_{0-\infty}$	Area under the serum concentration versus time curve extrapolated to infinity according to the following equation: $AUC_{0-\infty} = AUC_{0-t} + C_t / \lambda_z$ Values with a percentage of extrapolation >20% of $AUC_{0-\infty}$ will not be considered in the descriptive statistics
$\lambda_z$	Terminal elimination rate constant (see $t_{1/2}$ below)
$t_{1/2}$	Terminal half-life associated with the terminal phase determined according to the following equation: $t_{1/2} = 0.693 / \lambda_z$ where $\lambda_z$ is the slope of the regression line of the terminal phase of the serum concentration versus time curve, in semi-logarithmic scale. $\lambda_z$ will be calculated by taking the regression of at least 3 points.
CL	Total body clearance of a drug from the serum calculated using the following equation: $CL = \text{Dose} / AUC_{0-\infty}$
MRT	Mean residence time of the drug in the body calculated as: $MRT = AUMC_{0-\infty} / AUC_{0-\infty}$ where $AUMC_{0-\infty}$ is area under the serum concentration moment ( $C \cdot t$ ) versus time curve extrapolated to infinity according to the following equation: $AUMC_{0-\infty} = AUMC_{0-t} + (C_t \cdot t / \lambda_z + C_t / \lambda_z^2)$
$V_z$	Volume of distribution during the terminal phase calculated using the following equation: $V_z = \text{Dose} / (\lambda_z \cdot AUC_{0-\infty})$
$V_{ss}$	Steady state volume of distribution following IV dosing calculated as: $V_{ss} = MRT \cdot CL$

#### 8.4 IMMUNOGENICITY

Antibodies to XTMAB-16 will be evaluated in serum samples collected from all participants according to [Table 8](#). Additionally, serum samples should also be collected at the final visit from participants who discontinue from the study. Instructions for the collection and handling of biological samples will be provided by the Sponsor in a separate Laboratory Manual. These samples will be tested by the Sponsor or Sponsor's designee. Each serum sample will be divided into 2 aliquots (1 each for primary and a back-up).

Serum samples will be tested in a multi-tiered approach. A validated screening assay for antibodies binding to XTMAB-16 will be initially used to assess serum samples. Samples that are determined putative positive in the screening assay will then be subjected to a confirmatory assay to demonstrate that antibodies are specific to XTMAB-16. Samples that are identified as positive in the confirmatory assay will be further characterized in a validated tier assay and titer of confirmed positive samples will be reported. Other analyses may be performed to verify the stability of antibodies to study treatment and/or to further characterize the immunogenicity of study treatment. Serum samples will be screened for antibodies binding to XTMAB-16 and the titer of confirmed positive samples will be reported.

The detection and characterization of antibodies to XTMAB-16 will be performed using a validated assay method by or under the supervision of the Sponsor. The analytical methods used to measure immunogenicity will be described in a separate bioanalytical report. Only samples which are within the window of sample stability will be analyzed.

Samples that are confirmed positive for antibodies binding to XTMAB-16 may be further evaluated for their ability to neutralize the activity of the study treatment using a validated assay method.

Blood samples for PK/ADA/nAb will be collected for analysis from participants who experience an SAE that is also considered related to study treatment.

Blood volumes for ADA/nAB samples will be included in the Laboratory Manual.

#### 8.5 BIOMARKERS

Whole blood samples will be collected for measurement of exploratory circulating biomarkers according to [Table 8](#) and serum will be used for analysis. Circulating biomarkers that will be evaluated include ACE, sIL-2R, IL-6, and sTNF $\alpha$ .

Instructions for the collection and handling of biological samples will be provided by the Sponsor in a separate Laboratory Manual. The actual date and time (24-hour clock time) of each sample will be recorded in the eCRF. Data collected from analyses of circulating biomarkers may be used to correlate exposure to safety or other parameters or after the study.

Measurement of circulating biomarkers will be performed using a fit-for-purpose qualified assay method. The analytical methods used to measure these biomarker endpoints will be

described in separate bioanalytical reports. Only samples that are within the window of sample stability will be analyzed.

Blood collection volumes for biomarker samples will be included in the Laboratory Manual.

## 8.6 ADVERSE EVENTS AND SERIOUS ADVERSE EVENTS

### 8.6.1 DEFINITION OF ADVERSE EVENTS

An AE is any untoward medical occurrence associated with the use of an intervention in humans, whether or not considered intervention-related (21 CFR 312.32 (a)).

An AE can therefore be any unfavorable and unintended sign (including an abnormal laboratory finding), symptom, or disease (new or exacerbated) temporally associated with the use of study treatment.

### 8.6.2 DEFINITION OF SERIOUS ADVERSE EVENTS

An AE or suspected adverse reaction is considered "serious" if, in the view of either the Investigator or Sponsor, it results in any of the following outcomes:

- Death
- Life-threatening AE
- Inpatient hospitalization or prolongation of existing hospitalization
- A persistent or significant incapacity or substantial disruption of the ability to conduct normal life functions
- A congenital anomaly/birth defect

Important medical events that may not result in death, be life-threatening, or require hospitalization may be considered serious when, based upon appropriate medical judgment, they may jeopardize the participant and may require medical or surgical intervention to prevent one of the outcomes listed in this definition. Examples of such medical events include allergic bronchospasm requiring intensive treatment in an emergency room or at home, blood dyscrasias or convulsions that do not result in inpatient hospitalization, or the development of drug dependency or drug abuse.

### 8.6.3 CLASSIFICATION OF AN ADVERSE EVENT

#### 8.6.3.1 SEVERITY OF EVENT

The Investigator will make an assessment of severity for each AE and SAE reported during the study and assign it to 1 of the following categories:

**Mild** – Events require minimal or no treatment and do not interfere with the participant's daily activities.

**Moderate** – Events result in a low level of inconvenience or concern with the therapeutic measures. Moderate events may cause some interference with functioning.

**Severe** – Events interrupt a participant's usual daily activity and may require systemic drug therapy or other treatment. Severe events are usually potentially life-threatening or incapacitating. Of note, the term “severe” does not necessarily equate to “serious”.

#### 8.6.3.2 RELATIONSHIP TO STUDY INTERVENTION

All AEs must have their relationship to the study drug assessed by the Investigator who examines and evaluates the participant based on temporal relationship and his/her clinical judgment. The degree of certainty about causality will be graded using the categories below. In a clinical trial, the study drug must always be suspect.

- **Related** – The AE is known to occur with the study drug, there is a reasonable possibility that the study drug caused the AE, or there is a temporal relationship between the study drug administration and the event. Reasonable possibility means that there is evidence to suggest a causal relationship between the study drug and the AE.
- **Not Related** – There is not a reasonable possibility that the administration of the study drug caused the event, there is no temporal relationship between the study drug and event onset, or an alternate etiology has been established.

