#### 4.1.2 STOPPING RULES

##### 4.1.2.1 CRITERIA

Participants who experience injection site reactions or vital signs changes of Grade 1 or 2 (see [Appendix 4](#)) during infusion may continue infusion or have infusion interrupted for treatment and then resumed, at the discretion of the Investigator. Participants who experience injection site reactions or vital signs changes of Grade 3 or 4 during infusion should have infusion terminated and will be treated, as needed, for the adverse events. Any participant who experiences anaphylaxis during infusion will have infusion terminated; diagnosis of and recommended treatment for anaphylaxis is provided in [Appendix 5](#).

In addition to the assessment of SAEs and the occurrence/severity of other AEs by the Sponsor and the Investigator, after exploring potential confounding factors, the following criteria should be considered as guidance for the decision to stop dose escalation or to stop administration of the study drug to additional participants:

- 1 SAE for which the relationship to treatment cannot be reasonably excluded
- 1 AE of severe intensity for which the relationship to treatment cannot be reasonably excluded
- 3 or more participants with AEs of moderate intensity for which the relationship to treatment cannot be reasonably excluded
- 1 participant in a cohort with potential Hy's Law values
  - ALT or AST  $>8 \times$  upper limit of normal (ULN)
  - ALT or AST  $>5 \times$  ULN for more than 2 weeks
  - ALT or AST  $>3 \times$  ULN and (total bilirubin  $>2 \times$  ULN or INR  $>1.5$ )
  - ALT or AST  $>3 \times$  ULN with the appearance of fatigue, nausea, vomiting, right upper quadrant pain or tenderness, fever, rash, and/or eosinophilia ( $>5\%$ )
- QTcF  $\geq 500$  ms (men and women)
- Any other clinically significant intolerance findings

If any of the above occur, the Contract Research Organization (CRO) and Sponsor should be notified within 24 hours of becoming aware of the event. Decisions to stop dose escalation or stop administration of study drug to additional participants will be determined collectively between the PI, CRO Medical Monitor, and Sponsor.

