#### 9.4.2.2 ADVERSE EVENTS

Safety variables will be analyzed for all study participants in the Safety Set.

Adverse events will be coded by system organ class (SOC) and preferred term (PT) using the Medical Dictionary for Regulatory Activities (MedDRA) version 23 or higher.

The frequency of all AEs during the study will be presented for each cohort and treatment separately by SOC and PT. The data will be displayed as the number of participants experiencing the AEs, percentage of participants, and the number of events.

All TEAEs (defined as those AEs with an onset date/time on or after the start of infusion on Day 1 to end of safety follow-up), serious and nonserious, including deaths, will be tabulated and listed. Laboratory safety parameters that are reported as AEs will also be tabulated and listed.

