4.11.1 Adverse Events

An AE is any untoward medical occurrence in a study participant administered an IMP which does not necessarily have a causal relationship with this treatment.

A treatment-emergent adverse event (TEAE) is defined as an AE that begins or that worsens in severity after at least one dose of the study drug has been administered.

All related TEAEs will be defined as Adverse drug reaction (ADR).

Any AEs with incomplete start and end dates/times will be treated as follows:

- Adverse events with unknown start times, but with start date known, will be imputed with a time of 00:00, unless the start date corresponds to any given dosing date. In this case the start time will be imputed with the time of dosing. If this results in a start date/time after end date/time of the AE, then the time will also be imputed with 00:00.
- Adverse events with completely unknown start dates will be imputed with the date and time of first dosing, unless the end date is known and prior to dosing; in that case the start date will be imputed as the date of Screening and a time of 00:00.
- Adverse events with partially known start dates/times will be treated as follows:
 - If only the day is missing, then the day will be imputed with the first day of the month, unless the month and year in which the AE started is a month and year in which study drug was administered, then the day will be imputed with the first day on which study drug was administered in that month. If this results in a start date after the end date, then the day will be imputed with the first day of the month.
 - If only the month is missing, and the year is a year in which study drug was administered, then the month will be imputed with the first month in which study drug was administered. If this results in a start date after the end date of the AE, then the month will be imputed with JAN. If the known year part is not a year in which study drug was administered, then the month will also be imputed with JAN.
 - If both the day and month is missing and the year is a year in which study drug was administered, then the day and month will be imputed with the day and month of dosing. If this results in a start date after end date, then the day and month will be imputed with 01JAN. If the year is not a year in which study drug was administered, then the day and month will also be imputed with 01JAN.
 - If only the year is missing, then the year will be imputed with the year of dosing.

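### The Related and Not Related definitions overlap with no precedence rule, so the ADR count depends on which limb the assessor applies

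*Protocol*

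**What the plan says.** Protocol 8.6.3.2 has a two-category causality scale, and each category is a list joined by *or*.

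- **Related**: the event is known to occur with the drug, or a causal link is reasonably possible, "or there is a temporal relationship between the study drug administration and the event".
- **Not Related**: a causal link is not reasonably possible, "there is no temporal relationship between the study drug and event onset, or an alternate etiology has been established".

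The same section has the investigator assess "based on temporal relationship and his/her clinical judgment", and adds: "In a clinical trial, the study drug must always be suspect". It gives no time limit for a temporal relationship and no order of precedence between the lists.

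Protocol 9.4.2.2 defines TEAEs by "onset date/time on or after the start of infusion on Day 1 to end of safety follow-up". SAP 4.11.1 states: "All related TEAEs will be defined as Adverse drug reaction (ADR". That section shows ADRs in the adverse event overview. It also tabulates TEAEs by relationship, counting a participant with repeated events of one preferred term under the strongest causality.

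The stopping guidance in Protocol 4.1.2.1 uses a different expression, for example "3 or more participants with AEs of moderate intensity for which the relationship to treatment cannot be reasonably excluded". It neither uses the two category names nor cites 8.6.3.2.

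**The concern.** A binary causality scale should place each event in exactly one category. This one does not. A documented common cold after dosing is Related by timing and Not Related because its cause is established. Two careful assessors can grade it in opposite ways and both comply.

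The design enlarges the problem. There is a single infusion on Day 1, follow-up runs to Day 71, and every TEAE falls after the infusion began. With no window on timing, the third limb of Related can be read as true for any TEAE. The drug has not been given to humans before, so the known-to-occur limb gives little help and timing carries more weight.

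At stake is the meaning of the ADR row in the overview and of the by-relationship table. A reader will take these as the events attributable to the drug. Under the written definitions they may instead reflect which limb the assessor applied.

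**Working it through.** The documents give no figure to reproduce here. The check is logical, followed by simple arithmetic on group sizes.

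**1. The definitions as logic.** Let K = known to occur with the drug, P = reasonable possibility, T = temporal relationship, A = alternate etiology established.

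- Related = K or P or T
- Not Related = (not P) or (not T) or A

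**2. Post-dose events, with timing accepted (T true).** Related is then always true, whatever K is. Not Related reduces to (not P) or A.

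| Reasonable possibility | Other cause established | Related | Not Related |
|---|---|---|---|
| yes | no | met | not met |
| yes | yes | met | met |
| no | no | met | met |
| no | yes | met | met |

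Three of the four combinations meet both definitions, and none meets Not Related alone. These are counts of logical cases, not probabilities of events.

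**3. Is T true for every TEAE?** Under Protocol 9.4.2.2 a TEAE starts on or after the start of infusion. Under SAP 4.11.1 it begins or worsens after dosing. Either way it follows the dose. The text sets no limit that would make a late event fail T, although an assessor could judge that it does. So T can be read as true for all TEAEs but does not have to be.

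**4. Consequence for the ADR count.** If timing is applied as written, ADR = TEAE in every group, including placebo, since the assessor is blinded. If an established other cause or absence of a reasonable possibility prevails, only the first row of the table stays Related. Both readings comply with the text. The reported count can therefore lie anywhere between the first-row events and all TEAEs.

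**5. Sensitivity of the percentages.** Protocol Table 2 gives 9 active and 3 placebo per cohort. SAP 4.2 pools placebo, giving 3 + 3 = 6. If regrading changes one participant's ADR status, incidence moves by:

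- dose group: 1/9 = 11.1 percentage points
- pooled placebo: 1/6 = 16.7 percentage points

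**6. What does not move.** The safety endpoints in Protocol section 3 and SAP 3.2.1 include the incidence of TEAEs and SAEs. These do not use the causality grade.

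**The case against.** The strongest reply is that the wording permits over-attribution but does not require it. The assessor also uses clinical judgement, Protocol 8.6.4 limits causality assessment to people qualified to diagnose, and Not Related is open for many of the same events. An inclusive default suits a first-in-human study. TEAEs are tabulated whatever their causality, over-attribution would also show in the placebo column, and no hypothesis is tested. All of this stands, and it limits the consequence to the ADR and by-relationship displays. It does not remove the overlap: when both definitions are satisfied, judgement has no rule to apply.

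A reader might go further and infer that nearly every TEAE will be called a drug reaction and that background illness will then halt escalation. The documents do not support this. The 4.1.2.1 criteria have their own test, exclude mild events other than those that are serious or meet the liver, QTcF or other intolerance criteria, and are guidance applied after confounders are explored. The decision is collective. Under 4.1.2.2, meeting a criterion leads to unblinding of the participants concerned, but a stop is required only if 3 or more of them had active drug and none had placebo.

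The arithmetic shows the gap. Assume no drug effect, a background probability p of a moderate event per participant (the documents give none), and every such event counted as related.

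- Moderate-event criterion, P(X ≥ 3) with X ~ Bin(12, p). At p = 10%: 1 − 0.9¹² − 12(0.1)(0.9¹¹) − 66(0.01)(0.9¹⁰) = 11.1%. At 5%, 15% and 20% it is 2.0%, 26.4% and 44.2%.
- Required-stop pattern, P(at least 3 of 9 active) × (1 − p)³. At p = 10%: 0.0530 × 0.729 = 3.9%. At 5% and 20% it is 0.7% and 13.4%.
- If only a quarter of these events are counted, the moderate-event criterion is met with probability 0.3% at p = 10% and 2.0% at p = 20%.

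These figures describe the worst reading under assumed rates. They do not measure the defect in 8.6.3.2, because 4.1.2.1 is not tied to that grade. What remains is that an event graded Related would hardly be called reasonably excluded, and the protocol does not say whether the two judgements are the same.

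**Conclusion.** The point holds for the causality scale and for the ADR outputs built on it. This is a stated rule that gives an unreliable result, not a missing detail. The overlap follows from the text alone and needs no assumption. That the ADR count can approach the TEAE count rests on reading timing without a limit, which the text allows but does not compel. With 9 per dose and 6 on pooled placebo, a few regraded participants would visibly change the ADR percentages.

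No effect on the stopping criteria is established; on those, the sections only need to be reconciled. The correction is worth making because it is cheap and because the SAP tables cannot repair inconsistent grades afterwards.

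**What to change.** Before causality grading starts, revise Protocol 8.6.3.2 so that the two categories are mutually exclusive, with a stated precedence for events that meet limbs of both. One way is a single reasonable-possibility test in which timing is one consideration among others. Carry the same wording into the eCRF guideline so that the SAP's ADR category inherits one definition.

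Separately, reconcile 8.6.3.2 with 4.1.2.1 by stating whether those criteria use the 8.6.3.2 grade or a separate judgement. No change to the stopping criteria is proposed.

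The cost is protocol and eCRF-guideline wording. The downside is that reported ADR counts may be lower than under the literal timing-alone reading. All adverse events are still recorded regardless of relationship, as Protocol 8.6.4 requires.
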